X. Primary Safety Analysis

The primary safety analysis evaluated the composite event rate of all cause mortality and all cause hospitalization at 50 weeks. The statistical hypothesis is that the proportion of subjects in the treatment group where an event occurs by the 50 weeks will be non-inferior to the proportion of subjects where an event occurs by the 50 weeks in the control group. The statistical hypothesis to be tested is:

$$H_0: \pi_t > \pi_c + \delta$$

vs.

$$H_1: \pi_t \leq \pi_c + \delta$$

where $\delta=0.125$ (clinically insignificant difference) and π_c is the event rate in the control group and the π_t is the event rate in the treatment group. The statistical test to be used shall be the Blackwelder (1982) non-inferiority test and will be evaluated based on the intent-to-treat subject population.

The events comprising the composite primary safety endpoints are provided in the table below for all patients, for patients grouped by core lab ejection fraction (< 25 or ≥ 25), and patients grouped by core lab ejection fraction and NYHA (equal to 3 or not).

Table X.1 Primary Safety Events (Deaths or All Cause Hospitalizations) for the ITT Population

Group	Control n/N (%)	Optimizer n/N (%)	P-Value ¹
All	103/213 (48.36)	112/215 (52.09)	0.0348
BL EF ² <25	50/99 (50.50)	56/98 (57.14)	0.2041
BL EF ² \geq 25	53/113 (46.90)	56/117 (47.86)	0.0399
BL EF ² <25 & NYHA \neq 3	9/14 (64.29)	7/11 (63.64)	0.2484
BL EF ² <25 & NYHA=3	41/85 (48.24)	49/87 (56.32)	0.2805
BL EF ² \geq 25 & NYHA \neq 3	11/16 (68.75)	4/8 (50.00)	.00696
BL EF ² \geq 25 & NYHA=3	42/97 (43.30)	52/109 (47.70)	0.1219

¹One-sided Blackwelder's test for non-inferiority with $\delta = 0.125$

²One Control patient did not have a baseline core laboratory ejection fraction

There were 103 events in the control group and 112 events in the Optimizer group by 50 weeks. If one applies the Blackwelder test to the ITT population, assuming those lost to follow-up did not have an event, the rate in the control arm is $103/213 = 0.4836$ and in the test arm is $112/215=0.5209$. The difference is 0.0374 and the Blackwelder z-statistic is -1.8143 which corresponds to a P-value of 0.0348. The upper one-sided 95% confidence limit is 11.68 which is below the delta of 12.5. Under this test, the primary safety endpoint is met.

Recognizing that 6 control patients and 7 Optimizer patients either died or withdrew early with no follow-up beyond the screening examination, the modified ITT

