The one control and 3 of the 4 Optimizer patients experienced events so the number of events for the PP population is 102 in the control group and 109 in the Optimizer group. An analysis of the primary endpoint with the PP population yields 102/206 = 0.4951 in the control group and 109/204 = 0.5343 in the Optimizer group. The difference is 0.0392 and the Blackwelder z-statistic for this test is -1.7400 which corresponds to a P-value of 0.0409. The upper one-sided 95% confidence limit is

[figure not shown]
12.03 which is below the delta of 12.5. Under this test in the PP population, the primary safety endpoint is met.

Thus the primary safety null hypothesis is rejected under any of the three test conditions, ITT, m-ITT, or PP.

XI. Secondary Safety Analyses

Kaplan-Meier (KM) analyses were done for the composite for all patients in the ITT, m-ITT, and PP populations. The KM analysis for all ITT subjects appear in the figure below. The freedom from event curves with not statistically different from each other with a log-rank P-value = 0.2229.

Figure 1. Kaplan Meier Analysis of the Composite Primary Safety Endpoint of Death of Hospitalization in 350 days for the ITT Population.

[figure not shown]
The table below presents the freedom from even rates and 95% confidence intervals.

Table XI.1 Estimated Rates of Freedoms from Primary Safety Event through 350 Days (ITT)

Treatment Group	Month	Patients Remaining	Proportion Free from AE	Lower 95% CL	Upper 95% CL
Control	0	212	1	--	--
	1	193	0.9239	0.8880	0.9598
	3	169	0.8177	0.7652	0.8702
	6	131	0.6424	0.5769	0.7079
	12	67	0.4988	0.4302	0.5674
Optimizer	0	209	1	--	--
	1	181	0.8270	0.7756	0.8784
	3	147	0.7109	0.6492	0.7726
	6	120	0.5803	0.5131	0.6475
	12	92	0.4630	0.3950	0.5310

The KM analysis of the m-ITT population is presented in the figure and table below. The two curves were not significantly different from each other with a log-rank P-value of 0.2134.

Figure 2. Kaplan Meier Analysis of the Composite Primary Safety Endpoint of Death of Hospitalization in 350 days for the m-ITT Population.

[figure not shown]
The table below presents the freedom from event rates and 95% confidence intervals.

Table XI.2 Estimated Rates of Freedom from Primary Safety Event through 350 Days (m-ITT)

Treatment Group	Month	Patients Remaining	Proportion Free from AE	Lower 95% CL	Upper 95% CL
Control	0	207	1	--	--
	1	191	0.9227	0.8862	0.9592
	3	168	0.8169	0.7640	0.8698
	6	131	0.6407	0.5752	0.7062
	12	67	0.4974	0.4288	0.5660

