Optimizer	0	208	1	--	--
	1	171	0.8221	0.7702	0.8740
	3	147	0.7067	0.6448	0.7686
	6	120	0.5769	0.5097	0.6441
	12	92	0.4603	0.3925	0.5281

The KM curve for the PP population is presented in the figure and table below. Two freedom from event curves are not statistically significantly different from each other with a log-rank P-value of 0.2460.

Figure 3. Kaplan Meier Analysis of the Composite Primary Safety Endpoint of Death of Hospitalization in 350 days for the PP Population.

The table below presents the freedom from even rates and 95% confidence intervals.

Table XI.3 Estimated Rates of Freedoms from Primary Safety Event through 350 Days (PP)

Treatment Group	Month	Patients Remaining	Proportion Free from AE	Lower 95% CL	Upper 95% CL
Control	0	206	1	--	--
	1	190	0.9223	0.8858	0.9588
	3	168	0.8199	0.7674	0.8724
	6	131	0.6438	0.5781	0.7095
	12	67	0.4999	0.4311	0.5687
Optimizer	0	208	1	--	--
	1	169	0.8284	0.7767	0.8801
	3	146	0.7157	0.6538	0.7776
	6	119	0.5833	0.5157	0.6509
	12	91	0.4644	0.3958	0.5330

A Cox regression multivariate analysis was done on the primary safety endpoint (all cause mortality and hospitalization) for events through 350 days.

Variables were screened by the method of Hosmer and Lemeshow (2000) with a P-value for admission into competition for the final model of 0.2. Univariate Cox models including the covariate of interest and its interaction with treatment were used for screening. If the interaction term with treatment is not significant, a second model was done without the interaction to screen for the main effect.

The variables that were screened and their corresponding P-values are presented in the table below.

Table XI.4 Univariate Cox Regression Model Screening of Covariates for Primary Safety Events through 350 Days from Study Start Date (m-ITT)

Characteristic	P-value ¹
Age	0.0785
Age by Optimizer Treatment Interaction	0.8009

Gender	0.3246
Gender by Optimizer Treatment Interaction	0.4149
Baseline PVO2	0.9940
Baseline PVO2 by Optimizer Treatment Interaction	0.4311
Baseline AT	0.8637
Baseline AT by Optimizer Treatment Interaction	0.7270
Baseline Peak RER	0.5796
Baseline Peak RER by Optimizer Treatment Interaction	0.8730
Baseline Ejection Fraction (Quantitative)	0.6542
Baseline Ejection Fraction by Optimizer Treatment Interaction	0.9854
Baseline Ejection Fraction (Categorical Cut at 25)	0.4676
Baseline Ejection Fraction by Optimizer Treatment Interaction	0.6737
Diabetes	0.0982
Diabetes by Optimizer Treatment Interaction	0.2642

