Baseline NYHA (Site)	0.0779
Baseline NYHA by Optimizer Treatment Interaction	0.2845
Baseline NYHA (Site) (NYHA = 3 or Not)	0.0779
Baseline NYHA by Optimizer Treatment Interaction	0.2845
CHF Etiology	-- ²
CHF Etiology by Optimizer Treatment Interaction	-- ²
Baseline MLWHFQ	0.0445
Baseline MLWHFQ by Optimizer Treatment Interaction	0.2504
BMI	0.7600
BMI by Optimizer Treatment Interaction	0.8891
Race (White)	0.7382
Race by Optimizer Treatment Interaction	0.0506
PTCA or CABG	0.3363
PTCA or CABG by Optimizer Treatment Interaction	0.2056
Baseline Core Lab Exercise Duration	0.0912
Baseline Core Lab Exercise Duration by Optimizer Treatment Interaction	0.3932
Pseudo-Site	0.5091
Pseudo-Site by Optimizer Treatment Interaction	0.7444

¹Covariates with P-values ≤ 0.20 are allowed to enter the competition for the final model (bold face in table). If the interaction is not significant, the P-value reported is for the model with the main effect only.

²The model for CHF etiology did not have a solution so no P-value is reported.

The final model appears was determined by manual backward elimination and the result is presented in the table below. Eight variables were included in the competition for the final model including age, diabetes, baseline NYHA (continuous or categorical), baseline MLWHFQ, race, and race by treatment interaction.

Table 2.2.6 Multivariate Cox Regression Final Model Results for Mortality

Factor	Hazard Ratio	95% CL on HR	P-Value*
Race (White)	0.712	0.535-0.947	0.0197

The treatment term was the last term removed from the model and its P-value at removal was 0.1627. This analysis implies that the only covariate associated with the primary safety composite endpoint of all cause death or hospitalization is race with Caucasians having a lower risk of death or hospitalization than non-Caucasians. Stepwise regression was applied to provide a verification of this models and the same model resulted from that application.

XII. Primary Effectiveness Analysis

For the primary effectiveness analysis, imputation was necessary to obtain study outcomes for patients that did not have an endpoint at 24 weeks. The imputation was done by the methods described in Section IX above. Ten imputations for the ITT patients appear in the tables below. First the means are presented and then the responder analysis (with a responder defined a subject whose AT increased by $\geq 20\%$).

Table XII.1a Mean AT at Study Time Points

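### The secondary Cox model for the safety composite drops the randomised treatment by backward elimination, so it reports no device hazard ratio or confidence interval

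*Combined protocol and SAP*

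**What the plan says.** Section XI (Secondary Safety Analyses) of the Statistical Analysis Report introduces the model as follows: "A Cox regression multivariate analysis was done on the primary safety endpoint (all cause mortality and hospitalization) for events through 350 days". Candidate covariates, each with its interaction with treatment, were screened one at a time, "with a P-value for admission into competition for the final model of 0.2". Table XI.4 labels this screening as m-ITT. Selection then went on by hand: "The final model appears was determined by manual backward elimination and the result is presented in the table below". No rule protects the treatment term, and the outcome for it is given in one sentence: "The treatment term was the last term removed from the model and its P-value at removal was 0.1627".

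The final table (numbered 2.2.6) has a single row: race (White), hazard ratio 0.712, 95% limits 0.535 to 0.947, P = 0.0197. The text infers that "the only covariate associated with the primary safety composite endpoint of all cause death or hospitalization is race". The table's title, "Multivariate Cox Regression Final Model Results for Mortality", does not match the composite endpoint described in the text.

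The other time-to-event results in Section XI are Kaplan-Meier proportions by arm with 95% limits, and log-rank tests for ITT ("log-rank P-value = 0.2229"), m-ITT (0.2134) and PP (0.2460). None comes with a hazard ratio.

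**The concern.** In a randomised trial the arm is the contrast of interest. It is not one candidate predictor among many. Once it is eliminated, the model can describe risk factors but cannot give an adjusted comparison of device and control.

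The safety hypothesis (protocol IX.A.2; report Section X) is non-inferiority. For that question, failing to reach significance says little, and what informs is the estimate and how far its interval extends. A reader of Section XI gets a P-value for the removed term, a sentence about race, and three non-significant log-rank tests. The size of the device effect in time-to-event form, and the uncertainty around it, are missing.

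**Working it through.** **Inputs.** Events: "There were 103 events in the control group and 112 events in the Optimizer group by 50 weeks", so 103 + 112 = 215. Table X.2 shows the same events in m-ITT (207 control, 208 Optimizer), and 50 weeks is 350 days. P at removal is 0.1627. The Kaplan-Meier values are from Table XI.2 (m-ITT).

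**1. The one hazard ratio that is reported.** SE = [ln 0.947 − ln 0.535] / (2 × 1.96) = 0.5710 / 3.92 = 0.1457. z = ln 0.712 / 0.1457 = −2.332, two-sided P = 0.0197. This agrees with the report and indicates two-sided Wald P-values.

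**2. What P = 0.1627 would imply.** Treatment went last and race remained, so the model at that step held treatment and race. A treatment estimate therefore existed. Assume a two-sided Wald test, near-equal arms, proportional hazards and the direction seen in the Kaplan-Meier tables:

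- SE(ln HR) ≈ 2 / √215 = 0.1364; z = 1.396.
- ln HR = 1.396 × 0.1364 = 0.1904, so HR ≈ 1.21.
- 95% CI: exp(0.1904 ± 1.96 × 0.1364) = 0.93 to 1.58.
- With the SE from step 1 (0.1457) instead: 1.23 (0.92 to 1.63).
- The same method on the m-ITT log-rank P of 0.2134 gives 1.18 (0.91 to 1.55).

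The fitted value needs patient data.

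**3. Month 1, m-ITT.** Event-free: control 0.9227 (0.8862 to 0.9592), Optimizer 0.8221 (0.7702 to 0.8740). The intervals do not overlap, and the same holds in ITT and PP. SEs from the limits are 0.0730 / 3.92 = 0.0186 and 0.1038 / 3.92 = 0.0265. The difference is 0.1006 with SE √(0.0186² + 0.0265²) = 0.0324, so z ≈ 3.1.

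**4. Are hazards proportional?** The cumulative-hazard ratio is ln S(Optimizer) / ln S(control). The interval ratio uses the change in ln S since the previous time point.

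| Month | Control | Optimizer | Cumulative ratio | Interval ratio |
|---|---|---|---|---|
| 1 | 0.9227 | 0.8221 | 2.43 | 2.43 |
| 3 | 0.8169 | 0.7067 | 1.72 | 1.24 |
| 6 | 0.6407 | 0.5769 | 1.24 | 0.84 |
| 12 | 0.4974 | 0.4603 | 1.11 | 0.89 |

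The Optimizer proportion is lower at every tabulated point after baseline. The excess hazard sits in the first months, and the interval ratios fall below 1 after month 3. A single hazard ratio would average over this pattern.

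**5. The etiology factor.** Table XI.4 reports that the model for CHF etiology could not be solved. In binary form, Table VI.2 gives 142 + 139 = 281 ischemic and 428 − 281 = 147 non-ischemic among all randomised patients. Table IX.3 already uses a binary version in the propensity model.

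**The case against.** Much of the opposing case stands.

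- **The primary safety result is separate.** The Section X risk differences have one-sided 95% upper limits of 11.68, 12.15 and 12.03 points (ITT, m-ITT, PP) against a margin of 12.5, and none comes from the Cox model. A reader might infer that the missing hazard ratio undermines the non-inferiority conclusion. It does not.
- **No planned analysis was breached.** Protocol IX.A.2 plans Kaplan-Meier curves and log-rank tests. IX.A.5 calls for adjusted repeats only after significant baseline differences, and Section VI of the report finds none between arms. The Cox model can fairly be read as risk-factor modelling.
- **The report does not say that the device has no effect.** It discloses the removal and its P-value, and covariate may have been meant to exclude treatment. The proportions by arm let a reader see the early difference. The fault is an omission and a sentence open to misreading.
- **Counts differ from proportions.** At month 12 more Optimizer than control patients remain (92 against 67 in m-ITT). Only the estimated event-free proportions are lower at each time point.
- **The etiology failure is unexplained.** A reader might blame the very small categories in Table VI.2. The report gives no reason, so this is conjecture.

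None of this supplies the missing estimate. A model without treatment cannot show whether the arms differ, whatever purpose it was built for.

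**Conclusion.** The point holds as a reporting and modelling weakness in a secondary safety analysis. The randomised term was removed on its P-value, and the readable text gives no device hazard ratio or interval, adjusted or unadjusted. The figures and a few pages before the baseline tables were not available, so an annotation there cannot be excluded.

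On size, a hazard ratio of about 1.21 (0.93 to 1.58) is what P = 0.1627 would imply with 215 events. It rests on a two-sided Wald test, proportional hazards and a direction borrowed from the Kaplan-Meier tables. A reader might take it as a stable device effect. Step 4 argues against that, with a cumulative-hazard ratio that falls from 2.43 at month 1 to 1.11 at month 12. Nor can the upper limit be read as failing non-inferiority, because the documents set a margin on 50-week proportions and none on the hazard ratio. What the figures support is narrower: the data are compatible with anything from a slightly lower to a clearly higher average hazard on the device, with the excess concentrated early, and Section XI does not quantify this.

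**What to change.** 1. Keep treatment in the Cox model regardless of its P-value, and apply selection only to the other covariates.
2. Include the binary ischemic/non-ischemic factor. Section II of the report says randomisation was stratified by center as well, so handle center or pseudo-site as far as the data allow. Check the etiology coding first: the counts labelled ischemic in Table VIII.2 (32 + 115 = 147) equal the non-ischemic total from Table VI.2.
3. Report the treatment hazard ratio with its 95% CI, with a proportionality check or period-specific estimates, for example before and after month 1 or month 3.
4. Reword the race sentence so that it describes the covariates in the selected model and does not imply that the device is unrelated to the composite. Correct the table title in the same edit.

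The cost is one refit on existing data and one revised paragraph. The primary safety result does not change.
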